#### **6.9.6 PERMANENT DISCONTINUATION OF STUDY TREATMENT**

Patients may discontinue study medication for the following reasons:

- Confirmed radiographic disease progression
- Unacceptable adverse experiences as described in Table 2
- Intercurrent illness that prevents further administration of treatment
- Investigator's decision to withdraw the subject
- The subject has a confirmed positive serum pregnancy test
- Non-compliance with trial treatment or procedure requirements
- Completed 24 months of uninterrupted treatment with pembrolizumab or 35 administrations of study medication, whichever is later
- Confirmed complete response (CR) and treated for at least 24 weeks with pembrolizumab and had at least two treatments with pembrolizumab beyond the date when the initial CR was declared.

A subject may be granted an exception to continue on treatment with confirmed radiographic progression if clinically stable or clinically improved.

24 months of study medication is calculated from the date of first dose. Subjects who stop pembrolizumab after 24 months may be eligible for up to one year of additional study treatment if they progress after stopping study treatment provided they meet the requirements detailed in Section 5.6.

Date of permanent discontinuation and the reason will be recorded.

#### **6.9.7 Withdrawal from Study**

Withdrawal from the study refers to discontinuation of study treatment and study procedures and can occur for the following reasons:

- Patient decision
- Loss to follow-up
- Death
- Administrative reasons.

CUPem	C/37/2017	Imperial College London	V7.0, 08.12.2021
-------	-----------	----------------------------	------------------

After the end of treatment, each subject will be followed for 30 days for adverse event monitoring (serious adverse events will be collected for 90 days after the end of treatment as described in Section 7. Subjects who discontinue for reasons other than progressive disease will have post-treatment follow-up for disease status until disease progression, initiating a non-study cancer treatment, withdrawing consent or becoming lost to follow-up. Subjects who are discontinued from treatment, but have not progressed at that time, will still be under follow-up for study events of interest (unless lost-to-follow-up or withdrawal of consent). After documented disease progression each subject will be followed by telephone for overall survival until death, withdrawal of consent, or the end of the study, whichever occurs first.

If a patient dies whilst participating in the study a “Statement of Death” eCRF must be completed. The following details will be collected: date of death, whether autopsy performed, whether death was related to the disease under investigation, primary cause of death, secondary cause of death, and any other details.

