#### 3.3.1 Dose Modification (Escalation/Titration/Other)

Adverse events (both non-serious and serious) associated with pembrolizumab exposure may represent an immunologic aetiology. These adverse events may occur shortly after the first dose or several months after the last dose of treatment. Pembrolizumab must be withheld for drug-related toxicities and severe or life-threatening AEs as per Table 2 below. Also see Section 6.9 for supportive care guidelines.

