### 5.5.1 Survival Follow-up

Once a subject experiences confirmed disease progression or starts a new anti-cancer therapy, the subject moves into the survival follow-up phase and should be contacted by telephone every 12 weeks to assess for survival status until death, withdrawal of consent, or the end of the study, whichever occurs first.

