**Table 3: Table of Assessments**

Trial Period:	Screening Phase	Treatment Cycles								End of Treatment	Post-Treatment		
Treatment Cycle/Title:	Study Screening	1	2	3	4	To be repeated beyond 8 cycles				Discon	Safety Follow-up	Follow Up Visits	Survival Follow-Up
						5	6	7	8				
Scheduling Window (Days):	-28 to -1		± 3	± 3	± 3	± 3	± 3	± 3	± 3	At time of Discon	30 days post discon	Every 8 weeks post discon	Every 12 weeks
Administrative Procedures													
Pre-screening Visit													
Informed Consent	X												
Inclusion/Exclusion Criteria	X												
Demographics and Medical History	X												
Prior and Concomitant Medication Review	X	X	X	X	X	X	X	X	X	X	X		
Trial Treatment Administration		X	X	X	X	X	X	X	X				
Trial Treatment Compliance		X	X	X	X	X	X	X	X				
Quality of Life Questionnaire (EORTC QLQ-C30)	X					X				X			
Post-study anticancer therapy status											X	X	X
Survival Status		X	X	X	X	X	X	X	X	X	X	X	X
Clinical Procedures/Assessments													
Review Adverse Events	X	X	X	X	X	X	X	X	X	X	X		
Full Physical Examination	X a	X			X				X	X	X		
Directed Physical Examination	X a	X	X	X	X	X	X	X	X	X	X	X	
Vital Signs and Weight	X a	X	X	X	X	X	X	X	X	X	X	X	
ECOG Performance Status	X a	X	X	X	X	X	X	X	X	X	X	X	
Laboratory Procedures/Assessments: analysis performed by LOCAL laboratory													
Pregnancy Test –Serum β-HCG	X b		X c		X c		X c		X c				
PT/INR and aPTT	X d	X e	X e	X e	X e	X e	X e	X e	X e	X	X	X	
CBC with Differential	X d	X e	X e	X e	X e	X e	X e	X e	X e	X	X	X	

CUPem	C/37/2017	Imperial College London	V7.0, 08.12.2021
-------	-----------	----------------------------	------------------

Trial Period:	Screening Phase	Treatment Cycles								End of Treatment	Post-Treatment		
Treatment Cycle/Title:	Study Screening	1	2	3	4	To be repeated beyond 8 cycles				Discon	Safety Follow-up	Follow Up Visits	Survival Follow-Up
						5	6	7	8				
Scheduling Window (Days):	-28 to -1		± 3	± 3	± 3	± 3	± 3	± 3	± 3	At time of Discon	30 days post discon	Every 8 weeks post discon	Every 12 weeks

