### 7.2 Adverse Event recording

AEs will be collected throughout the study, from the point of consent until the Safety Follow Up visit\*; they will be followed up according to local practice until the event has stabilised or resolved, or the follow-up visit, whichever is sooner. Serious Adverse Events (SAEs) will also be recorded throughout the study. See Appendix D for further details.

At the Safety Follow Up visit, any AEs of Grade > 1 which remain unresolved will be followed up by the Investigator until the resolution of the AE to Grade 0-1 or until the beginning of a new anti-neoplastic therapy, whichever occurs first, but without further recording in the eCRF.

\*SAEs, including death that occur within 90 days of the end of treatment or before initiation of a new anti-cancer treatment should also be followed and recorded.

Details to be collected in the eCRF for each AE will include:

- AE description
- Date of onset and date of resolution
- Severity
- Seriousness
- Relationship to study treatment

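### SAEs are to be collected for 90 days after treatment, but no AE or SAE review is scheduled after the 30-day visit, so up to 60 of the 90 days have no scheduled SAE enquiry

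*Protocol*

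**What the plan says.** **The window.** Protocol 6.9.7 sets two periods: "After the end of treatment, each subject will be followed for 30 days for adverse event monitoring", and "serious adverse events will be collected for 90 days after the end of treatment". Protocol 7.2 follows the same split. For AEs in general, "AEs will be collected throughout the study, from the point of consent until the Safety Follow Up visit". Its footnote adds that "SAEs, including death that occur within 90 days of the end of treatment or before initiation of a new anti-cancer treatment should also be followed". SAP 5.3 repeats that footnote.

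**The schedule.** In Protocol Table 3 the row "Review Adverse Events" is marked at screening, Cycles 1 to 8, discontinuation and the Safety Follow-up, which Protocol 5.4 places about 30 days after the last dose. It is blank for the 8-weekly Follow Up Visits and the 12-weekly Survival Follow-Up. SAP Table 2 has the same marks.

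**Later contacts.** Patients who stop without progression are seen every 8 weeks (Protocol 5.5). After confirmed progression or new therapy, the patient "should be contacted by telephone every 12 weeks to assess for survival status" (Protocol 5.5.1).

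**Late events.** Protocol 3.3.1 says of immune-related events: "These adverse events may occur shortly after the first dose or several months after the last dose of treatment".

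**The concern.** The text promises a 90-day SAE record, but the schedule that sites work from stops asking at about day 30. Because the protocol itself expects immune-related events months after the last dose, days 31 to 90 are not a period that can be assumed quiet.

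The SAE summaries (SAP 6.5 and shell Tables 9 to 11) would be read as covering 90 days, with no note that the method of ascertainment changes at day 30. SAP 6.8 would not reveal the problem: it counts missing observations, and an event that nobody asked about leaves no missing value. At stake are the completeness of the late safety record and, where an event surfaces late, the speed of reporting.

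**Working it through.** No power or error-rate calculation applies, and the plan states no figure to reproduce. The check sets the windows against the schedule and counts days.

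**Inputs.** SAE window: 90 days (Protocol 6.9.7, 7.2; SAP 5.3). Last scheduled AE review: about day 30 (Protocol 5.4, Table 3). Follow Up Visits: every 8 weeks, ±7 days (Protocol 5.5). Survival calls: every 12 weeks (Protocol 5.5.1).

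**1. Uncovered part of the window.** 90 − 30 = 60 days; 60/90 = 0.67. This is a maximum. If the window ends at new anti-cancer therapy, it is shorter for patients who start such therapy before day 90.

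**2. Marks after discontinuation, by row of Table 3.**

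| Row | Safety Follow-up | Follow Up Visits | Survival Follow-Up |
|---|---|---|---|
| AE review | yes | no | no |
| Directed examination, vital signs, ECOG | yes | yes | no |
| Blood count, coagulation, thyroid | yes | yes | no |
| Serum chemistry | yes | no | no |
| Survival status | yes | yes | yes |

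**3. Patients without progression.** Counting from discontinuation, the first Follow Up Visit is at 8 × 7 = day 56 (range 49 to 63) and the next at 16 × 7 = day 112. One clinical visit falls inside days 31 to 90. Days 57 to 90 are seen only in retrospect.

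**4. Patients in survival follow-up.** If survival follow-up starts at discontinuation, the first call is at 12 × 7 = day 84. It is later if progression or new therapy comes later: a start at day 50 puts the call at 50 + 84 = day 134. On this count the first call falls by day 90 only if survival follow-up starts by day 90 − 84 = 6. The planning medians for PFS are 2 months (null) and 4 months (alternative) (Protocol 8.2), so progression should be a common route off treatment and this group is unlikely to be small.

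**5. Share of SAEs missed.** Let f be the share of post-treatment non-fatal SAEs that start after day 30, and c the share of those that reach the site without a scheduled enquiry. The share missed is f × (1 − c). Neither document gives f or c, so the 67% of days cannot be turned into a percentage of events.

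**The case against.** The strongest reply is that the schedule table is not the only safeguard.

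- **Clinical visits continue for some patients.** The 8-weekly visits include examination, vital signs, ECOG status, blood count, coagulation and thyroid tests. A reader might infer that every later contact covers only survival and disease status, or that late events are found only if volunteered. Table 3 does not support that for patients without progression. It does show no AE item at those visits, and no serum chemistry, although the hepatic event of clinical interest in Protocol 7.10 is defined by chemistry and reportable to day 90.
- **Progressed patients still have the mandatory 30-day safety visit** (Protocol 5.4). This stands; the gap begins after it.
- **Deaths are tracked** through survival status and a dedicated death form (Protocol 6.9.7). This also stands, and limits the point mainly to non-fatal events.
- **General duties exist.** Protocol 5.9.7 says AEs are monitored throughout the study but defers to Section 7. Protocol 7.4.2 requires SAE reporting within 24 hours of awareness, and reporting of apparently drug-related information even after a patient has completed the study. Protocol 6.9.7 keeps non-progressed patients under follow-up for certain events it does not define. These set an intention and a deadline; none schedules an enquiry.
- **Manuals not available here** (Pharmacovigilance, eCRF Completion) may prompt the question. That is possible. If they do, the schedules in the protocol and SAP should still agree with them.
- **Overlap with the 8-week AE endpoint.** That endpoint has its own shortfall against 30-day collection, 56 − 30 = 26 days. Correcting it would still leave days 57 to 90 of the SAE window uncovered.

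**Conclusion.** The mismatch stands. SAE collection is required to day 90, the last scheduled AE or SAE review is at about day 30, and up to 60 of 90 days have no scheduled enquiry. The effect is greatest in telephone survival follow-up and smaller for patients without progression, who have one clinical visit at about day 56. The likely consequence is under-ascertainment of non-fatal SAEs.

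A reader might go further and state what percentage of SAEs would be lost. The documents do not support this: any figure would come from assumed onset times and reporting rates, and its effect on the full SAE tables would be diluted by on-treatment events.

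The conclusion assumes that Table 3 and SAP Table 2 are the full list of scheduled enquiries and that contacts are counted from discontinuation. It does not touch the efficacy analyses. It is worth correcting because the remedy is cheap and delivers the plan's own safety rule.

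**What to change.** Reconcile Protocol 5.5.1, 6.9.7, 7.2 and Table 3 with SAP 5.3 and Table 2:

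1. In both schedules, mark an SAE review at the existing Follow Up Visits and at the first Survival Follow-Up contact, asking back over the period to day 90 after the last dose.
2. State whether the SAE window closes at the start of new anti-cancer therapy. If so, the question asks back only to that date. State also the day from which the 90 days run, since the text refers variously to end of treatment, last dose and discontinuation.
3. Amend 5.5.1 and 6.9.7 so that the survival call and the follow-up visit include the question.

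**Cost.** One extra question at contacts that already take place, with no added visit, plus a small eCRF change and a protocol amendment.

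**Limit.** Where the first survival call falls after day 90, ascertainment is retrospective: the record becomes more complete, but reporting is not faster.

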#### **6.9.8 Procedures for Withdrawal from Study**

If the patient is withdrawn from the study the date of withdrawal and the reason must be recorded. When a subject discontinues/withdraws prior to trial completion, all applicable activities scheduled for the final trial visit should be performed at the time of discontinuation, unless the patient is too unwell to attend the clinic. Any adverse events which are present at the time of discontinuation/withdrawal should be followed in accordance with the safety requirements outlined in Section 7. Subjects who a) attain a CR or b) complete 24 months of treatment with pembrolizumab may discontinue treatment with the option of restarting treatment if they meet the criteria specified in Section 5.6. After discontinuing treatment following assessment of CR, these subjects should return to the site for a Safety Follow-up Visit (Section 5.4) and then proceed to the Follow-Up Period of the study (section 5.5).

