#### Hypothesis:

Pembrolizumab has Efficacy in CUP:

- as a second-line treatment in terms Response which translates into improved PFS and OS.
- and treatment leads to rapid improvement in QOL in high metastatic disease burden.

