##### **Cohort 2:**

Cohort 2 is now formally closed. This cohort had sought to enrol patients who are chemo-naïve (first-line setting) for CUP, with a PS 0-2.

\*\*\*\*\*

Patients will undergo screening procedures during a standard 28-days time window from initiation of the study, under standard GCP and informed consent. Restaging will be performed by computerized tomography using ir-RECIST criteria at 3 months from initiation of systemic treatment and on an 8 weekly basis thereafter until radiological proven disease progression or intolerance or patient choice.

The EORTC QLQ-C30 questionnaire (to assess the quality of life) will be done at baseline after 3 months and then at discontinuation of study treatment.

Correlative translational study samples (blood) and tissue (used for histological confirmation and to document PD-L1 expression) will be collected at baseline, and blood and serum samples monthly (after an informed optional consent and banked for retrospective immune-modulating and other biomarkers for future research and analysis). Patients will also be separately consented to the NHSE CUP 100K genome project that will be running in the UK by 2018, for deep sequencing of tumor tissue and germ-line, in centers participating in, or with access to the UK framework for this programme.

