#### **5.9.14 Quality of Life**

The QOL instrument, EORTC QLQ-C30 version 3 will be administered as specified in Table 3 and must be completed before other assessments are performed or study drug is administered.

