5.1 Primary Efficacy Endpoint

The overall response to treatment is assessed using RECIST v1.1 and immune-related (irRECIST). Appendices A and B in the protocol present the guidelines for evaluation of objective tumour response Using RECIST 1.1 (Response Evaluation Criteria in Solid Tumours) or immune-related RECIST. The disease control rate will be calculated.

Disease Control Rate (DCR) - is defined as the proportion of patients in whom the best overall response is determined as complete response (CR), partial response (PR) or stable disease (SD) for at least 12 weeks in either RECIST or irRECIST criteria.

Overall Survival (OS) - defined as the length of time from study enrolment until death, withdrawal of consent, last follow-up date if lost to follow-up or the end of the study, whichever occurs first.

Progression Free Survival (PFS) – is defined as the length of time from study enrolment to first evidence of progressive disease identified at follow-up or confirmed disease progression at the end of the trial or death. Patients will be censored at the last follow-up date if they are lost to follow-up, withdrawn from the study or have not progressed at the end of study. Median PFS and its 95% confidence interval will be reported. Kaplan-Meier survival curves will also be plotted.

Quality of Life (QOL) is measured as scores from the EORTC QLQ-C30 version 3 questionnaire which will be administered at baseline, after 3 months and then at discontinuation of study treatment.

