6.8 Missing Data

No imputation for missing data will be undertaken. The number of missing observations for each variable will be reported.

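### Section 6.9.8 excuses the discontinuation visit for patients too unwell to attend and no other route exists for the QLQ-C30, so the discontinuation quality-of-life result may be too favourable

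*Protocol*

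**What the plan says.** Protocol 6.9.8 deals with patients who discontinue or withdraw before the trial is complete. The activities of the final visit "should be performed at the time of discontinuation, unless the patient is too unwell to attend the clinic". It names no substitute for those who cannot come. The same section still requires the date and reason for withdrawal and the follow-up of adverse events that are present. Survival follow-up also continues: under 5.5.1 patients "should be contacted by telephone every 12 weeks to assess for survival status".

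Protocol 3.1 states that the QLQ-C30 "will be done at baseline after 3 months and then at discontinuation of study treatment". SAP 5.1 places quality of life under the primary efficacy endpoint, with the form "administered at baseline, after 3 months and then at discontinuation of study treatment". Table 3 of the protocol marks it at screening, cycle 5 and discontinuation, and not at the safety, follow-up or survival follow-up contacts. Protocol 5.9.14 says that the form "will be administered as specified in Table 3 and must be completed before other assessments are performed or study drug is administered". The hypothesis under the primary objectives (protocol 2.1) includes "and treatment leads to rapid improvement in QOL in high metastatic disease burden".

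SAP 6.3 compares scores between visits by repeated measures ANOVA or Friedman's test, in per-protocol patients who have a baseline form and at least one later form. SAP 6.9 removes from this analysis patients who withdraw before two cycles, or before a follow-up tumour or quality-of-life assessment. SAP 6.8 states: "No imputation for missing data will be undertaken". It adds that the number of missing observations will be reported.

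**The concern.** The condition for missing the visit is being too unwell, which is close to what the questionnaire measures. The listed reasons for stopping treatment include progression, unacceptable adverse events and intercurrent illness (protocol 6.9.6), so some patients will be ill at exactly that point. If their forms are absent and the analysis uses the forms in hand, the discontinuation column describes patients fit enough to travel. A real decline could look smaller, or no change could look like a gain, in an outcome that the trial ties to its primary hypothesis. The form is a self-report questionnaire and sites already telephone patients, so part of this loss looks avoidable.

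**Working it through.** The documents give no quality-of-life sample size, expected change, SD or completion rate, so there is no stated figure to reproduce. The check is a reading of the text followed by arithmetic for scale.

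**1. Forms available.** Protocol 3.1, SAP 5.1 and SAP 6.3 agree on three time points, and the SAP's Table 5 shell has only baseline, month 3 and discontinuation columns. That leaves two post-baseline forms in the analysis. A discontinuation form that is not completed at the visit is not scheduled again.

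**2. What the SAP does with a missing form.** A patient with neither post-baseline form drops out of the quality-of-life analysis (SAP 6.3, 6.9). A patient with a month-3 form but no discontinuation form stays in the set but is absent from the discontinuation mean. No sensitivity analysis addresses the reason for absence. Repeated measures ANOVA and Friedman's test in their usual form also need all three forms per patient.

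**3. How many could depend on the discontinuation form alone.** Inputs are the null and alternative median PFS of 2 and 4 months and the sample size range of 31 to 67 (protocol 8.2). Exponential PFS is an assumption: S(t) = 0.5^(t/median), with t = 84/30.4375 = 2.76 months for week 12.

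| Median PFS | S(week 12) | Progressed or dead | Of 31 | Of 67 |
|---|---|---|---|---|
| 2 months | 0.384 | 62% | 19.1 | 41.3 |
| 4 months | 0.620 | 38% | 11.8 | 25.5 |

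At 3 calendar months the shares are 65% and 40%. These are shares of progression or death, not of early stopping. Patients who have died can give no form. Protocol 6.9.6 lets some continue after progression. The first planned CT is at 12 weeks, so a patient with unnoticed progression may still reach the month-3 form. The figures show that the group could be large, not how large it is.

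**4. Size of the bias.** Let m be the share of discontinuation forms missing and D the mean gap between patients with and without a form. The full mean is (1 − m) × (mean with form) + m × (mean without form), so the observed mean exceeds it by m × D. Both m and D are assumptions, on a scale taken as 0 to 100 with higher meaning better.

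| m | D = 10 | D = 20 | D = 30 |
|---|---|---|---|
| 10% | 1 | 2 | 3 |
| 20% | 2 | 4 | 6 |
| 30% | 3 | 6 | 9 |
| 40% | 4 | 8 | 12 |

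**5. A second illustration.** A simulation took a true mean change of −10 (SD 20), with the log-odds of a missing form rising by 0.05 for each point of worse change. With 10%, 22% and 30% missing, the observed means were −8.1, −6.2 and −4.9. They are too favourable by 1.9, 3.8 and 5.1 points, which lies within the range above. All these parameters are assumed.

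**The case against.** The strongest reply is that the clause is not the cause. Patients too ill to travel miss clinic forms whatever 6.9.8 says, and deleting it would bring none of them in. That stands. The gap is the lack of another way to complete the form, of a recorded reason when it is absent, and of an analysis that allows for informative absence. Neither document forbids remote completion, but neither provides for it, and 5.9.14 ties the form to the Table 3 visits.

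The weight of the outcome can also be questioned. Quality of life is in the hypothesis and in SAP 5.1, but not among the listed primary objectives. The trial calls itself hypothesis generating and is sized on PFS and OS. The hypothesis speaks of rapid improvement, which the month-3 form addresses more directly. This limits the consequence but does not remove it, because SAP 6.3 tests across all visits.

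Several stronger readings are tempting and are not supported:

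- A reader might infer that every safeguard is waived at discontinuation. Adverse event follow-up, the date and reason, survival follow-up and counts of missing values all remain.
- A reader might infer that the form is missing in the sickest and that quality of life is overstated by a known amount, or turn this into a loss of power. The documents give no completion rate, score gap or SD. A power comparison against full return would also assume forms from patients who die, decline or are still on treatment at study end.
- A reader might infer that nothing can be done once forms are lost. Month-3 scores, ECOG status and the recorded reason for stopping can support sensitivity analyses, although these rest on assumptions that the data cannot test.
- Table 3's heading about repetition beyond 8 cycles might imply further forms for patients who stay on treatment. The SAP analyses none, and they would not help patients who stop early.

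**Conclusion.** The point holds as a risk, not as a demonstrated bias. Followed as written, the plan lets the absence of the discontinuation form depend on how ill the patient is, offers no second route, and then analyses the available forms without imputation. The discontinuation mean and the comparison across visits may therefore be too favourable.

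The direction rests on the reasonable but undocumented assumption that patients too unwell to attend score worse. It also rests on reading the undefined final trial visit as the Table 3 discontinuation visit, which is natural because its activities are due when the patient discontinues. The range of 1 to 12 points is an illustration from assumed inputs, and the 38% to 62% depends on exponential PFS. This is a cheap improvement.

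**What to change.** - **Protocol 6.9.8 and 5.9.14:** state that a patient who cannot attend is still offered the QLQ-C30 at discontinuation by telephone, by post or at the bedside. Record the mode of completion and, if the form is not completed, the reason.
- **SAP 6.3:** report completion by visit, mode and reason. Add a sensitivity analysis for informative missingness for forms that are still absent, for example a mixed model with delta adjustment over a stated range.

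The cost is a short protocol amendment, two eCRF fields, an added SAP paragraph, and a call or posted form for some patients. The downsides are a small burden on ill patients, who may decline, and a minor difference between modes of administration. Remote completion will not reach everyone, which is why the sensitivity analysis is needed as well.
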